	
ASA), defined as the presence of argininosuccinic acid in the blood or urine, decreased AL enzyme activity in cultured skin fibroblasts or other appropriate tissue, or identification of a pathogenic mutation in the AL gene
 
A subject may not be included in the study if any one of the following criteria is met:
 
For both Group 1 and Group 2:
 
 - Current or prior Helicobacter pylori infection - Chronic gastrointestinal illness (e.g., inflammatory bowel disease) - Chronic renal failure - Taking probiotic medications within a week of study start date - Currently pregnant or lactating. Documentation of a negative pregnancy test within a week prior to testing is required, unless pre-menarchal or menopausal, experiencing menses that week, or other circumstances which preclude pregnancy (e.g. hysterectomy). - Presence of acute infection at the time of inclusion - Participation in any other clinical interventional trial or received experimental medication within the last 30 days - Any clinical or laboratory abnormality or medical condition that, at the discretion of the investigator, may put the subject at an additional risk by participating in this study
Treatment	
Agent-	Acetohydroxamic Acid (AHA, Lithostat)
Dosage, schedule, route of administration-	Single dose, 60 mg/kg PO
Safety Issues-	Bone marrow depression (leukopenia, anemia, and thrombocytopenia) has occurred in experimental animals receiving large doses of AHA. However, only a single dose will be administered in this study, and is not likely to result in this adverse effect.
Primary Outcome Measures:	Difference in the time-averaged level of blood $^{13}\text{CO}_2$ after a single bolus of intravenous [^{13}C]-Urea, measured on two occasions: once at baseline, and once 2-hr after an oral bolus of AHA
Secondary Outcome Measures:	Differences in blood [^{13}C]-Urea, Urea, Ammonia, Glutamine
Safety Variables	Hemoglobin, White blood count, platelets, AST, ALT, Bilirubin, Creatinine
Statistical Considerations (sample size and analysis plan):	Longitudinal linear regression models will assess and compare time averaged mean changes in blood $^{13}\text{CO}_2$, and blood levels of [^{13}C]-urea, ammonia and glutamine. A sample size of 8 crossover participants provides 90% power to detect a 20% relative difference in the time-averaged level of $^{13}\text{CO}_2$ in treatment with AHA versus non-AHA under a 2-tailed type I error of 0.05.

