4.4 Retention strategies

As the study involves only 2 days of participation, we anticipate retention to be near 100%.

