4.6 Schedule of Events

Subjects will be studied twice: once without and once with a single dose of acetohydroxamic acid, with the two study days at least 3-days apart.

Table 1. Laboratory investigations (each study day)

	Time point (min)							
	Baseline	0	30	60	90	120	180	240
Blood [¹³ C]-urea		X	X	X	X	X	X	X
Blood urea		X	X	X	X	X	X	X
Plasma glutamine		X	X	X	X	X	X	X
Ammonia		X	X	X	X	X	X	X
Blood ¹³ CO ₂		X	X	X	X	X	X	X
Urine [¹³ C]-urea		X						X
Urine urea		X						X
Safety labs:								
Hemoglobin	X							X
White blood count	X							X
Platelets	X							X
AST	X							X
ALT	X							X
Bilirubin	X							X
Creatinine	X							X

'Baseline' indicates at a time 0 on days when AHA is not administered or at a time prior to AHA administration on the days where AHA is administered. In addition, some of the blood and urine samples will be saved at the Clinical and Translational Science Institute at CNMC for up to 3 years after the conclusion of the study to test for the metabolism of AHA, after which the samples will be discarded.

5. Safety Monitoring

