5.7 Subject Discontinuation

An intent-to-treat approach will be used. All data acquired prior to termination for the reasons outlined below will be included in the primary analysis unless patient withdraws

consent. Every effort will be made to conduct a final study visit with the participant and participants will be followed clinically until, if applicable, all adverse events resolve.

- Withdrawal by the participant
- Withdrawal by the investigator
- Intercurrent illness or event that precludes further visits to the study site or ability to evaluate disease (e.g.-mental status change, large pleural effusion).

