5.8 Data Quality and Monitoring Measures

As much as possible data quality is assessed at the data entry point using intelligent on-line data entry via visual basic designed screen forms. Data element constraints, whether independent range and/or format limitations or 'relative' referential integrity limitations, can be enforced by all methods employed for data input. QA reports assess data quality post-data entry. As we note, data quality begins with the design of the data collection forms and procedures and incorporates reasonable checks to minimize transcription and omission errors. Of the more important quality assurance measures are the internal validity checks for reasonableness and consistency.

- Data Monitoring: The RDCRN DMCC identifies missing or unclear data and generates a data query to the consortium administrator contact.
- Data Delinquency Tracking: The Data Management and Coordinating Center will monitor data delinquency on an ongoing basis.

6. Statistical Considerations

Linear longitudinal regression models will be developed to estimate the change in the time-averaged levels of blood $^{13}\text{CO}_2$ (primary endpoint), as well as blood levels of [^{13}C]-urea, ammonia and glutamine after AHA versus after non-AHA. When we evaluate the effect of AHA on each metabolite, the model will control for each metabolite's pretreatment level and will adjust variance estimates to account for the correlation between measurements on the same person as well as to take account of the random effect on the intercept. We will consider a relative AHA versus non-AHA difference in the time-averaged level of $^{13}\text{CO}_2$ of at least 20% as a signal that AHA can effectively reduce the impact of gut bacteria on urease activity. The presence of a clear effectiveness signal in healthy adults will be required before the crossover study can be implemented in adults with UCD.

Pilot data indicates that the expected level $^{13}\text{CO}_2$ in the absence of AHA treatment is 0.041% with a conservative precision of +/- 0.0075%. Therefore, using the sampsi procedure in Stata 12, a sample size of 8 crossover participants provides 90% power in 2-tailed testing at an alpha of 0.05 to detect a 20% relative (0.041% versus 0.033%)

difference in the time-averaged level of $^{13}\text{CO}_2$ on AHA versus non-AHA in either healthy or UCD affected adults.

7. Data Management

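### Section 6 sets no small-sample reference distribution or degrees of freedom for a primary test on 8 people with one AHA contrast each, and the choice left open decides whether the test holds 5%

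*Combined protocol and SAP*

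**What the plan says.** Section 6 makes the time-averaged blood level of labelled CO2 the primary endpoint and compares it with and without AHA by linear longitudinal regression. The model has a random intercept and includes the pretreatment level of the metabolite concerned as a covariate. On the variance, it is to "adjust variance estimates to account for the correlation between measurements on the same person as well as to take account of the random effect". The synopsis describes the same approach in outline: "Longitudinal linear regression models will assess and compare time averaged mean changes in blood" labelled CO2 and the secondary metabolites.

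On size, section 6 says that "a sample size of 8 crossover participants provides 90% power in 2-tailed testing at an alpha of 0.05 to detect a 20% relative" difference, given as 0.041% versus 0.033%. The basis is pilot data in which the level "in the absence of AHA treatment is 0.041% with a conservative precision of +/- 0.0075"%. Section 4.6 fixes the structure: "Subjects will be studied twice: once without and once with a single dose of acetohydroxamic acid".

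For moving on to UCD subjects, section 6 takes a relative difference of "at least 20% as a signal that AHA can effectively reduce the impact of gut bacteria on urease activity". No p-value or interval is attached to that rule.

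Neither section 6 nor the synopsis names the estimator, the reference distribution, the degrees of freedom or a small-sample correction. Stata 12 is mentioned only for the sample-size calculation. The plan does not say whether the pretreatment level is one value per person or one per study day.

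**The concern.** AHA changes only between study days. The samples within a day make each day's average more precise but add no AHA contrasts, so the primary test rests on 8 within-person differences. A variance adjustment for same-person correlation is most naturally read as a person-clustered (sandwich) standard error. That does deal with same-day correlation, but with 8 clusters its usual large-sample form rejects too often.

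The same data can therefore pass or fail at 0.05 depending on an unstated choice: the critical value is 1.960 with z and 2.365 with t on 7 df. The confidence intervals move with it, and the secondary metabolites use the same model.

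**Working it through.** **Inputs from the documents.** 8 people per group, two-sided alpha 0.05, 90% power, 0.041% versus 0.033% (difference 0.008), precision 0.0075% (section 6); one AHA and one non-AHA day per person (section 4.6); time 0 plus six later samples per day (section 4.6, Table 1).

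**The stated power.** Take 0.0075 as the SD of the within-person difference. The standard error is 0.0075/√8 = 0.00265, the standardized difference is 0.008/0.00265 = 3.017, and the z formula gives Φ(3.017 − 1.960) = 85.5%, not 90%. If 0.0075 is instead each day's SD and the days are uncorrelated, the SD of the difference is 0.0075 × √2 = 0.0106 and the z formula gives 56.9%. A figure near 90% does come out if a between-day correlation of about 0.55-0.6 is assumed, or a correlation of about 0.3-0.35 between repeated samples. The documents give neither.

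**Type I error without the covariate (exact under normality).** In the balanced case the AHA estimate is the mean of 8 differences.
- With the n/(n−1) factor, the clustered statistic is the paired t statistic. Referred to z, its error is P(|t₇| > 1.960) = 9.1%.
- Without the factor, the statistic is larger by √(8/7), so the error is P(|t₇| > 1.960 × √(7/8)) = P(|t₇| > 1.833) = 10.9%.
- With the factor and t on 7 df, the error is 5%.

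**Type I error with the covariate (simulated).** No AHA effect, 8 people, 2 days, 6 samples per day, random-intercept fit with person-clustered standard error, 5,000 to 10,000 runs per setting. The person, day and residual variances are assumptions, varied across settings because the documents give none.

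| Pretreatment covariate | z, with n/(n−1) | z, uncorrected | t on 7 df, with n/(n−1) |
|---|---|---|---|
| None (exact) | 9.1% | 10.9% | 5% |
| One value per person | 9.0-9.7% | 11.0-11.5% | about 5% |
| One value per study day | 10.4-13.9% | 12.2-16.2% | 6-9% |

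Smaller separate checks widen the per-person z figure to about 8-10%.

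**Candidate replacements (simulated, 10,000 runs per setting).** t on the 8 differences, 7 df: 4.8-5.5%. With a period term, 6 df: 4.9-5.6%. A person-by-day random effect with the covariate gave 4.7-5.8% on t with 6 df and 9.6-11.0% with z. The 6 df stood in for a Kenward-Roger correction, which was not itself run.

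**Power and interval width for the replacement, if 0.0075 is the SD of the difference.** Noncentral t gives 73.5% (7 df) or 71.1% (6 df). The 95% half-width is 2.365 × 0.00265 = 0.0063 on 7 df, against 1.960 × 0.00265 = 0.0052 with z. For 90% power by t, that SD must be at most about 0.0059 (7 df) or 0.0057 (6 df).

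**The case against.** A reader might infer that this trial has a type I error of 9% to 16%. The documents do not support that. They never say z will be used, and the random intercept in the same sentence also allows a mixed model with small-sample degrees of freedom, which could hold close to 5%. What the text shows is an unspecified test; every rate above is conditional. This objection stands, and it limits the point to the omission and its consequences.

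A second objection also stands: the covariate figures depend on a definition the plan does not give. It would be wrong to say that t on 7 df always fails once the covariate is in the model. With one pretreatment value per person it holds about 5%; only a day-specific value leaves it at about 6-9%.

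A third is that this is a small pilot whose go rule carries no p-value. That limits the consequence. But section 6 does commit to two-tailed testing at 0.05 and justifies its sample size on that basis, so the calibration of the test is still part of the plan.

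A standard error taken from the random intercept alone is a further possible reading. Its error with z depends on day-to-day variation that the documents do not give: about 5-10% with none, 12-15% at an assumed day-level intraclass correlation of 0.1, and 23-27% at 0.3. This is sensitivity only.

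**Conclusion.** The point holds as an omission that matters at this sample size. The planned variance adjustment in its usual large-sample form exceeds 5% in every clustered-with-z setting examined: 9.1% without the covariate, about 8-10% with a person-level covariate and about 10-14% with a day-specific one, all with the n/(n−1) factor. The first figure needs only normality and balance; the others also rest on assumed variance components.

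Two further inferences should not be drawn. The decision to proceed to UCD subjects is not shown to be at risk, because the signal of at least 20% has no test attached. Nor is the stated 90% power shown to be wrong: the sampsi options and the meaning of the 0.0075% are not given, and the gap between 90% and 85.5% has nothing to do with the choice between z and t.

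This should be settled before the data are analysed. It is not a reason to hold the study.

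**What to change.** State as the primary test each person's AHA minus non-AHA difference in time-averaged labelled CO2, with t inference on the 8 differences: 7 df, or 6 df with a period term if order is randomized. This is on the same scale as the 20% signal. Use the same contrast for the secondary metabolites.

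Four items go with it:
- **Order.** Section 1.1 puts AHA on the second occasion; sections 4 and 10.1 describe randomized order. Reconcile them, because under a fixed order a period term cannot be separated from AHA.
- **Pretreatment covariate.** If it is kept, define it as a pre-AHA value. Table 1 in section 4.6 lists labelled CO2, ammonia and glutamine at time 0 but not at its separate pre-AHA Baseline, and section 10.1 gives the tracer 60 minutes after AHA. If time 0 is tracer time, the AHA-day value follows the dose and adjusting for it could remove part of the effect. The design figure was not available to settle this. Do not adjust for that value unless it is confirmed to be drawn before AHA.
- **People with one study day.** Section 5.7 says "All data acquired prior to termination for the reasons outlined below will be included in the primary analysis", yet one day gives no within-person difference. If the longitudinal model is kept for this reason, use a person-by-day random effect with a small-sample df correction, and check its size by simulation. Section 4.4 suggests that few people are affected: "As the study involves only 2 days of participation, we anticipate retention to be near 100"%.
- **Power.** Say what the 0.0075% is and restate the power for the chosen test.

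The paired test without a covariate needs SAP wording only and no new samples. Its cost, if 0.0075% is the SD of the within-person difference, is a half-width of 0.0063 on 7 df rather than 0.0052 with z, and a stated power of about 74% (7 df) or 71% (6 df) in place of 90%. A pre-AHA covariate on AHA days could need an extra draw if time 0 proves to be after the dose.

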7.1 Registration

Registration of participants on this protocol will employ an interactive data system in which the clinical site will attest to the participant's eligibility as per protocol criteria and obtain appropriate informed consent. IRB approval for the protocol must be on file at the DMCC before accrual can occur from the clinical site.

The DMCC will use a system of coded identifiers to protect participant confidentiality and safety. Each participant enrolled will be assigned a local identifier by the enrollment site. This number can be a combination of the site identifier (location code) and a serial accession number. Only the registering site will have access to the linkage between this number and the personal identifier of the subject. When the participant is registered to participate in the study, using the DMCC provided web-based registration system, the system will assign a participant ID number. Thus each participant will have two codes: the local one that can be used by the registering site to obtain personal identifiers and a second code assigned by the DMCC. For all data transfers to the DMCC both numbers will be required to uniquely identify the subject. In this fashion, it is possible to protect against data keying errors, digit transposition or other mistakes when identifying a participant for data entry since the numbers should match to properly identify the participant. In this fashion, no personal identifiers would be accessible to the DMCC.

7.2 Data Entry

Data collection for this study will be accomplished with online electronic case report forms. Using encrypted communication links, on-line forms will be developed that contain the requisite data fields.

7.3 Data Quality Control

As much as possible data quality is assessed at the data entry point. Data element constraints, whether independent range and/or format limitations or 'relative' referential integrity limitations, can be enforced by all methods employed for data input. QA reports assess data quality post-data entry. As we note, data quality begins with the design of the data collection forms and procedures and incorporates reasonable checks to minimize transcription and omission errors. Of the more important quality assurance measures are the internal validity checks for reasonableness and consistency. In addition to those described above, we propose to build these checks into the initial tables and cross tabulations that should reveal any remaining data quality issues.

7.4 Laboratory data flow

This study intends to collect a small number of samples on a small number of subjects. Some samples will be shipped via courier to Children's Hospital of Philadelphia. Given the trivial number of samples exchanged, online courier tracking and email exchange will be sufficient to ensure sending and receipt of samples.

7.5 Study Records Retention

Study records will be maintained for at least three years from the date that the grant federal financial report (FFR) is submitted to the NIH.

7.6 Protocol Deviations

A protocol deviation is any noncompliance with the clinical study protocol, Good Clinical Practice, or Manual of Procedures requirements. The noncompliance may be on the part of the subject, the investigator, or study staff. As a result of deviations, corrective actions are to be developed by the study staff and implemented promptly.

All deviations from the protocol must be addressed in study subject source documents and promptly reported to the DMCC, Study Chair, and the local IRB, according to their requirements.

8. Human Subjects

8.1 GCP Statement

This clinical trial will be conducted in accordance with the ethical principles that have their origin in the Declaration of Helsinki, and that are consistent with Good Clinical Practice and all applicable regulatory requirements.

8.2 Benefits

8.2.1 Potential Benefits of the Proposed Research to Subjects and Others

Subjects will be compensated for their participation in the study, and will receive \$500 for completion of the study (\$250 per day).

Additionally, if the proposed studies show that the use of AHA is effective in reducing hyperammonemia and increasing urea excretion in patients with urea cycle disorders, these patients can be treated for their deficiency long-term with the use of this new specific therapeutic agent pending regulatory approval. Thus, there can be an important direct benefit for these participants. If the proposed study and the underlying hypothesis are correct this study could improve the medical condition of some or all of the patients also prevent life-threatening events in those who respond. At this stage, the patients will have the option to be treated under a different specific IND obtained by their local physician or enroll in a long-term study if one is available. Thus, this significant potential benefit balances the relatively low risks of the study.

8.2.2 Importance of the Knowledge to Be Gained

The study will provide the first reliable information of whether AHA could potentially reduce the hyperammonemia associated with urea cycle disorders. Such knowledge could provide an additional treatment for hyperammonemia in these conditions. In addition, the information gained could also be relevant to better understanding the regulation of the urea cycle which may impact also treatment of hyperammonemia due to liver disease.

8.3 Recruitment

Children's National is a nation-wide referral center for patients with urea cycle disorders, and the lead site for the Urea Cycle Disorders Consortium. In addition, to recruiting patients with urea cycle disorders, our recently funded RDCRC-UCD has a centralized registry, where patients are invited to enroll in clinical trials. We are in close contact with the National Urea Cycle Disorders Foundation, a lay organization dedicated to the promotion of treatment and research to improve the health of patients with urea cycle disorders. The NUCDF will help with patient recruitment for these studies.

Inclusion of women and minorities

The urea cycle disorders studied in this trial involve both genders equally and all ethnic groups are affected to the best of our knowledge. Thus, there will not be exclusion of either gender or any ethnic group. The investigators of this study plan to make a special effort to enroll subjects from various ethnic groups in proportions consistent with their proportion in the general populations. The Washington D.C. metropolitan areas have large minority groups reflected also by their proportions in the patients seen at Children's National. We believe that the study will have adequate representation by women and minority groups.

The cohort of unaffected control subjects will be adults only, as participation in this trial will not confer any direct benefit to unaffected children.

8.4 Written Informed Consent

Written informed consent will be obtained from each participant before any study-specific procedures or assessments are done and after the aims, methods, anticipated benefits, and potential hazards are explained. The participant's willingness to participate in the study will be documented in writing in a consent form, which will be signed by the participant with the date of that signature indicated. The investigator will keep the original consent forms and signed copies will be given to the participants. It will also be explained to the participants that they are free to refuse entry into the study and free to withdraw from the study at any time without prejudice to future treatment. Written and/or oral information about the study in a language understandable by the participant will be given to all participants.

8.5 Process of Consent

Healthy adult control subjects will be recruited from the Washington DC metropolitan area. The study may be advertised on the campus of some local universities.

Participants with UCDC will be recruited from the metabolism clinics of Children's National, or through the Urea Cycle Disorders Consortium. Alternatively, patients will be notified of the study by a collaborating lay organization, the National Urea Cycle Disorders Foundation.

Informed consent will be obtained by one of the investigators of the study before the study can begin. The participants will receive a copy of the consent before the formal informed consent process takes place at the clinic or at the CRC. Consent forms will be signed by all participants (and legal guardian when appropriate) and the consent process will be documented in the patient's chart. The Research Subject Advocates of the CRCs will be present during some administrations of informed consent in this trial participating sites in order to assure that the informed consent process is conducted according to the highest ethical standards.

